For example, among subjects HPV 16 seronegative and PCR positive at Day 1 or HPV 18 seronegative and PCR positive at Day 1, the incidence of CIN 2/3 related to the relevant HPV type will be estimated in each treatment group and the 95% confidence intervals for these rates will be provided. Only cases of CIN that are detected following the Month 7 visit will be included in this analysis.

j. Assessment of Potential Waning of Vaccine Efficacy

Due to the timing between the development of HPV infection and the development of clinical sequelae, it is expected that the target number of cases required to estimate the vaccine efficacy with respect to the primary endpoint of the study at the interim analysis (19 cases) will be observed ~2.5 years into the study. By Year 4, it is anticipated that ~10 to 12 additional cases will be observed. Thus, there is limited power in this study to draw any definitive conclusions regarding changes in vaccine efficacy over time. Nevertheless, an exploratory analysis will be conducted to assess a possible waning of the vaccine efficacy. Specifically, at the conclusion of the study, the vaccine efficacy by year will be estimated, and any observed trends in the efficacy over time will be reported. The first year estimate will include all follow-up through Month 12 for each subject; the second year estimate will include all follow-up through Month 24 for each subject; the third year estimate will include all follow-up through Month 36 for each subject; and the final estimate will include all follow-up through Month 48 for each subject. A potential waning of vaccine efficacy will be explored using the per-protocol and first MITT populations.

D. Definition of Compliance Measure

Treatment compliance is defined in this study as receipt of all scheduled study vaccinations. To summarize treatment compliance, the numbers of subjects who receive each vaccination will be tabulated by treatment group. As stated in Section III.B., subjects who do not complete the full vaccination regimen will be excluded from the per-protocol primary analyses of efficacy but will be included in 2 MITT analyses.

Another important compliance measure in this study is the degree of subject compliance with follow-up visits following the completion of the vaccination series. Since colposcopy is a required procedure for the identification of potential study endpoints, subjects who miss study follow-up visits or who

D. Definition of Compliance Measure (Cont.)

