All summaries will be provided by treatment group and in total. However, in the by-treatment-group summaries, the treatment groups will be labeled as Group A and Group B unless the DSMB has a specific concern and requests that the groups be unblinded.

The interim summaries of safety will be performed on partially unscreened and unaudited data to ensure that the DSMB has the quickest access to the largest possible data set in any given summary. It is recognized that there may be minor changes in incidences and severity gradings of adverse experiences based on the screening and auditing process. However, since DSMB decisions with regards to safety are likely to be based on large, unexpected differences in safety parameters between treatment groups, such inaccuracies are not likely to result in incorrect decisions.

VII. STATISTICAL TECHNICAL ISSUES**A. Planned Statistical Power and Sample Size****1. Efficacy (Overall Study)**

In order to avoid problems with imprecise incidence and efficacy estimates, the efficacy study is powered based on a fixed event design with an interim analysis. To ensure adequate power for the interim analysis (80 to 90% power) and the final analysis ($\geq 90\%$) for varying true vaccine efficacies after the multiplicity adjustment, at least 19 cases of the primary endpoint are required for the interim analysis, and at least

A. Planned Statistical Power and Sample Size (Cont.)

29 cases are required for the final analysis. Table 7 gives the power for the primary efficacy analysis (based on the methodology described in Section VII.D.1.a.) for varying true vaccine efficacy values with 19 cases at the interim analysis and 29 cases at the final analysis.

Table 7

Power Sensitivity Analysis

Analysis	α -Level	Number of Cases	True Vaccine Efficacy	Power
Interim	0.0204	19	80%	80%
			85%	90%
			90%	97%
Final	0.0411	29	80%	95%
			85%	99%
			90%	>99%

An overall sample size of 11,500 subjects should yield at least 29 cases of the primary endpoint by the time all subjects have completed Month 48 of the study based on the following assumptions:

- a. ~18% of the subjects enrolled will be HPV 16 seropositive at Day 1 or PCR positive at Day 1 or Month 7;
- b. ~18% of the subjects enrolled will be HPV 18 seropositive at Day 1 or PCR positive at Day 1 or Month 7;
- c. the attrition rate will be no more than 15% through Month 7 of the study and no more than 5% per year thereafter;

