- d. all subjects followed beyond Month 7 are eligible to be endpoints and any subject who discontinues the study is at risk for HPV 16- or 18-related CIN 2/3 or worse for half of the study;
- e. the incidence of CIN 2/3 or worse related to HPV Type 16 will be ~0.19% in the placebo group over the 41 months after Postdose 3, while the incidence of CIN 2/3 or worse related to HPV Type 18 will be ~0.038% in the placebo group over the 41 months after Postdose 3; and
- f. if the vaccine efficacy is extremely high, all cases will have to accrue in the placebo group before the efficacy analysis may be performed.

A. Planned Statistical Power and Sample Size (Cont.)

[figure not shown]
Assuming that all subjects followed beyond Month 7 are eligible to be considered as endpoints, a sample size of 11,500 will provide ~8000 subjects who are eligible to be considered as cases according to the HPV 16-related disease definition and ~8000 subjects who are eligible to be cases according to the HPV 18-related disease definition. Since the primary endpoint is a composite endpoint, any subject who is eligible to be considered as an endpoint according to the HPV 16-related disease definition, the HPV 18-related disease definition or both will be included in the population at risk for the primary analysis. Therefore, assuming an ~8% overlap in the number of subjects who are HPV 16 or 18 seropositive at Day 1 or PCR positive Day 1 through Month 7, the population at risk for the primary analysis will include ~9000 subjects. Using a person time approach under assumptions (3) and (4) and given the event rates in assumptions (5) and (6), ~9000 subjects in the population at risk will provide the required number of endpoints by Year 4 of the study.

Figures 1 and 2 illustrate the derivation of the HPV 16-related CIN 2/3 cases and HPV 18-related CIN 2/3 cases, respectively, from the 11,500 subjects enrolled.

A. Planned Statistical Power and Sample Size (Cont.)

Figure 1

[figure not shown]
Derivation of HPV 16-Related CIN 2/3 Cases

A. Planned Statistical Power and Sample Size (Cont.)

Figure 2

Derivation of HPV 18-Related CIN 2/3 Cases

A. Planned Statistical Power and Sample Size (Cont.)**2. Immunogenicity (Consistency Lot Substudy)**

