All subjects in the study will be randomized in a 1:1 ratio to receive either quadrivalent HPV (Types 6, 11, 16, 18) L1 VLP vaccine or placebo within investigative sites. Within the quadrivalent HPV vaccine group, subjects will be further randomized to receive 3 different lots of the vaccine in a 1:1:1 ratio. The actual lots received will differ between subjects enrolled in the consistency lot substudy and the remaining subjects in Protocol 015.

Subjects participating in the consistency lot substudy will be randomized in a 1:1:1:3 ratio to receive Consistency Lot 1 of quadrivalent HPV (Types 6, 11, 16, 18) L1 VLP vaccine, Consistency Lot 2 of quadrivalent HPV (Types 6, 11, 16, 18) L1 VLP vaccine, Consistency Lot 3 of quadrivalent HPV (Types 6, 11, 16, 18) L1 VLP vaccine, or placebo within investigative sites. This randomization will ensure a 1:1:1 allocation of subjects to the 3 quadrivalent HPV (Types 6, 11, 16, 18) L1 VLP vaccine consistency lots. It will also maintain a 1:1 ratio of subjects receiving quadrivalent HPV (Types 6, 11, 16, 18) L1 VLP vaccine (any lot) and placebo for the overall efficacy study.

For the non-consistency lot part of the study, the Interactive Voice Response System (IVRS) will assign a block of 18 allocation numbers to a study site upon allocation of the first subject at that site. Within the block of 18 numbers, 9 will be allocated to vaccine (3 to Lot No. VAI018I001, 3 to Lot No. VAI025T001, and 3 to Lot No. VAI025T002) and 9 to placebo in a 3:3 ratio in blocks of 6. The system will assign an additional block of allocation numbers to a study site once it has depleted its supply of numbers.

For the consistency lot substudy, the IVRS will assign a block of 18 allocation numbers to a study site upon allocation of the first subject at that site. Within the block of 18 numbers, 3 will be allocated to Consistency Lot 1, 3 to Consistency Lot 2, 3 to Consistency Lot 3, and 9 to placebo in a 1:1:1:3 ratio in blocks of 6. The system will assign an additional block of allocation numbers to a study site once it has depleted its supply of numbers.

For both parts of the study, case numbers will be assigned to the subjects sequentially at each study site beginning with the lowest number available at the site as subjects are enrolled in the study. This will retain the randomization and the treatment group ratio within study sites. Case numbers should not be reassigned for any reason.

C. Blinding/Unblinding

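### The placebo incidences in assumption (e) of SAP VII.A.1, written as 41-month risks, give about 9 cases from 11,500 subjects, not the 29 claimed; they work only as rates per year

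*SAP*

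**What the plan says.** SAP Section VII.A.1 (Efficacy, Overall Study) sets the targets: "at least 19 cases of the primary endpoint are required for the interim analysis", and 29 for the final analysis. It then states that "An overall sample size of 11,500 subjects should yield at least 29 cases of the primary endpoint" by the time all subjects complete Month 48, given a list of assumptions (a) to (f).

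Assumption (e) supplies the event rates. For HPV 16, "the incidence of CIN 2/3 or worse related to HPV Type 16 will be ~0.19% in the placebo group over the 41 months", counted from Postdose 3. For HPV 18 the figure is about 0.038%, with the same 41-month period repeated. Assumption (f) adds that, if efficacy is extremely high, every case has to come from the placebo group.

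The text after the list derives about 8,000 eligible subjects per HPV type and about 9,000 in the population at risk. It refers to a person-time calculation and concludes that these "subjects in the population at risk will provide the required number of endpoints by Year 4 of the study".

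Two other places give timing. Section I.B.2 expects the interim target around Month 30 and the final target around Month 48. Section III.C.3.j expects 19 cases at about 2.5 years and says that by Year 4 "it is anticipated that ~10 to 12 additional cases will be observed".

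**The concern.** Month 7 to Month 48 is exactly 41 months, so assumption (e) as written gives the total placebo risk over the whole follow-up. A total risk of 0.228% in about 4,000 women is about 9 events. The section nevertheless says the assumptions yield 29.

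This pair of percentages is the only event rate offered to justify 11,500 subjects, the Month 30 and Month 48 timings, and the feasibility of both analyses. If the written figures were right, even the 19-case interim would be very unlikely to be reached by Month 48. If the targets and timings are right, the rate is misstated. Anyone comparing observed accrual with assumption (e) would then be using a benchmark about 3.4 times too low.

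**Working it through.** **Inputs, all from the SAP**
- 11,500 subjects (VII.A.1). Section VII.B: "All subjects in the study will be randomized in a 1:1 ratio", so 5,750 receive placebo.
- Excluded for HPV 16: "18% of the subjects enrolled will be HPV 16 seropositive at Day 1 or PCR positive at Day 1 or Month 7". The same 18% applies to HPV 18. This leaves 0.82 per type.
- Attrition of 15% through Month 7, then at most 5% per year (assumption c). Dropouts count as at risk for half the period (assumption d).
- Incidences of 0.0019 (HPV 16) and 0.00038 (HPV 18), sum 0.00228 (assumption e).
- Follow-up of 41 months = 41/12 = 3.417 years.

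**Step 1: reproduce the plan's denominators**
- Eligible per type: 11,500 × 0.85 × 0.82 = 8,016 (plan: about 8,000). Placebo: 4,008.
- Population at risk, with 8% positive for both types: 11,500 × 0.85 × 0.92 = 8,993 (plan: about 9,000).

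Both agree, so the denominators are not the source of the discrepancy.

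**Step 2: expected placebo cases with (e) as written**
- HPV 16: 4,008 × 0.0019 = 7.6
- HPV 18: 4,008 × 0.00038 = 1.5
- Total: 9.1

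Retention over 3.417 years is 0.95^3.417 = 0.839. The person-time fraction is 0.839 + 0.5 × (1 − 0.839) = 0.920, and 9.1 × 0.920 = 8.4. Linear 5% per year also gives 8.4.

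**Step 3: more generous variants of the same reading**

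| Variant | Expected cases |
|---|---|
| After attrition, adding vaccine cases at VE 90% to 80% | 9.2 to 10.1 |
| 4,500 placebo subjects at risk | 10.3 |
| All 5,750 placebo subjects, no exclusions | 13.1 |
| Both arms, 8,016 eligible, VE 0% | 18.3 |
| Both arms, 9,000 at risk, VE 0% | 20.5 |
| All 11,500 subjects, no exclusions, VE 0% | 26.2 |

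None reaches 29, even with zero efficacy and nobody excluded. With a Poisson mean of 8.4, the probability of 19 or more cases is about 0.001, and of 29 or more about 2 × 10⁻⁸. For 29 expected placebo cases on this reading, the trial would need 2 × 29 / (0.00228 × 0.920 × 0.82 × 0.85), or about 39,700 subjects.

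**Step 4: the same figures as rates per year**
- Without later attrition: 4,008 × 3.417 × 0.00228 = 31.2
- With attrition: 31.2 × 0.920 = 28.7 (HPV 16 23.9, HPV 18 4.8). Linear attrition gives 28.6.

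The 28.7 rounds to the plan's 29. The equivalent 41-month risks would be 0.19% × 41/12 = 0.65% and 0.038% × 41/12 = 0.13%.

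**Step 5: check against the stated timing**

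Month 30 is 23 months after Month 7. Assuming a constant hazard and the same attrition rule, the per-year reading gives 16.7 placebo cases. With vaccine cases at VE 90% to 80% the total is 18.4 to 20.0, close to the interim target of 19. The cumulative reading gives about 4.9 placebo cases. Section III.C.3.j implies 19 + 10 to 12 = 29 to 31 by Year 4, again in line with the per-year figures.

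**Step 6: power**

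The exact conditional binomial gives 80.1%, 90.9% and 97.6% at 19 cases and 95.9%, 99.1% and 99.9% at 29 cases, for VE 80%, 85% and 90%. This agrees with Table 7, so the error is confined to accrual.

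**The case against.** The strongest reply is that this is a slip in one phrase and not a failed design. The section says a person-time method was used and calls the inputs event rates, which suggests rates per unit time. On that reading the sample size, case targets and timings all fit together. The statements about 29 cases and about 10 to 12 later cases then need no correction. Much of this stands: the per-year reading is the likely intention, and Section III.C.3.j supports it.

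It is also true that the analyses are triggered by observed counts, so a misworded assumption changes neither how many cases occur nor the conditional power. The figure of 39,700 subjects applies only if 41-month risks were really meant, and the SAP describes no formal monitoring against assumption (e).

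Finally, Figures 1 and 2 could not be read in the copy reviewed, and Section I.B.2 attributes the timing to event rates in the protocol, which was not available. Either may carry the correct unit.

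None of this removes the contradiction. No readable text labels the figures as annual, and the 41-month period is stated for each type. If the figures or the protocol do give annual rates, they disagree with assumption (e), which would still need correcting.

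**Conclusion.** The point holds. As written, assumption (e) yields 9.1 expected placebo cases (8.4 after attrition) against the 29 said to follow from it, and it also falls short of the 19 for the interim. The two percentages reproduce the plan only as annual rates (28.7 after attrition), so the stated period is almost certainly wrong, by a factor of about 3.4.

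This rests on the SAP's own exclusion, attrition and allocation figures and, following assumption (f), on all cases arising in placebo; relaxing that does not rescue the written figure. The Month 30 comparison also assumes a constant hazard. The case targets, alpha levels and Table 7 power are not in question. The correction is necessary because this is the only rate supporting the sample size and the timing of both analyses.

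**What to change.** 1. Check the unit against Figures 1 and 2 and the protocol.
2. If annual rates were intended, restate assumption (e) as about 0.19 (HPV 16) and 0.038 (HPV 18) cases per 100 placebo person-years after Month 7.
3. Add the expected cumulative cases that follow: about 17 in placebo at Month 30 (18 to 20 in both arms at VE 90% to 80%) and about 29 in placebo at Month 48, with the attrition rule used.
4. If 41-month risks really were meant, state the expected count of about 9 and withdraw the claim that 11,500 subjects yield 29 cases, together with the timing that depends on it.
5. In the same edit, align the cross-references: the paragraph after the list cites assumptions (3) to (6), while the list is lettered (a) to (f).

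The cost is SAP wording only: one assumption line and the expected-case figures. On the annual reading, no population, test, alpha level or case target changes.

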Safety: The primary variables of interest for safety/tolerability are serious vaccine-related adverse experiences, if any occur, and severe, injection-site adverse experiences. Unless they are considered serious adverse events, reports of injection-site adverse experiences will only be solicited from subjects participating in the nonserious adverse experience substudy and from subjects enrolled in the United Kingdom. Subjects from any study site may spontaneously report such events, however.

Efficacy: The primary variable of interest for efficacy is the combined incidence of HPV 16-related CIN 2/3 or worse and HPV 18-related CIN 2/3 or worse. This endpoint will occur if on any single biopsy, endocervical curettage (ECC) or Loop Electrosurgical Excision Procedure (LEEP)/conization tissue block, the following occur:

- Pathology panel consensus diagnosis of: CIN 2, CIN 3 (including squamous carcinoma in situ), adenocarcinoma in situ, invasive squamous cervical carcinoma, or invasive adenocarcinoma of the cervix,

AND

- Detection of HPV 16 and/or HPV 18 by biopsy Thinsection PCR in an adjacent section from the same tissue block.

Of secondary interest are the incidences of colposcopic biopsy and definitive excisional cervical procedures (LEEP, laser conization, cold-knife conization) performed due to HPV 16- and 18-related cervical disease and the overall incidence of ALL CIN 2/3 and invasive cervical cancer (caused by any vaccine or non-vaccine HPV type).

Immunogenicity (Consistency Lot Substudy): For immunogenicity, the following endpoints are of primary interest: (1) the percentage of subjects who achieve anti-HPV 6 ≥ 200 mMU/mL, anti-HPV 11 ≥ 200 mMU/mL, anti-HPV 16 ≥ 200 mMU/mL, and anti-HPV 18 ≥ 200 mMU/mL at Week 4 Postdose 3 and (2) the geometric mean titers (GMTs) to HPV 6, 11, 16, and 18 at Week 4 Postdose 3. Of secondary interest are the GMTs to HPV 6, 11, 16, and 18 at Months 24 and 48. The anti-HPV 6, 11, 16, and 18 responses at Months 7, 24, and 48 will only be measured in the subjects participating in the consistency lot substudy.

Additional exploratory efficacy and immunogenicity endpoints will be summarized. These endpoints are described in the main body of the Data Analysis Plan in Section III.A. for efficacy and Section IV.A. for immunogenicity.

Data Analysis and Decision Criterion for Success of the Study

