The third MITT analysis will include all subjects who receive at least 1 dose of quadrivalent HPV (Types 6, 11, 16, and 18) L1 VLP vaccine or placebo and who have any follow-up visit after 1 month following the first injection, regardless of initial serology and PCR status.

The MITT populations consider incorrectly randomized subjects and subjects who received the incorrect clinical material in the analysis according to the treatment group to which they were randomized by the study allocation schedule.

C. Approaches to Efficacy Analysis**1. Primary Efficacy Hypothesis**

The interim and final primary efficacy analyses will be conducted when fixed numbers of cases of the primary endpoint have been observed. Specifically, the interim analysis will be conducted when at least 19 cases of the primary endpoint have been observed, and the final analysis will be conducted when at least 29 cases of the primary endpoint have been observed.

To address the primary hypothesis of the study, a one-sided test of the null hypothesis that the vaccine efficacy (defined as $100[1 - \text{Relative Risk}]$) is $\leq 0\%$ will be conducted. The alternative hypothesis is that the vaccine efficacy is $>0\%$. A point estimate of the vaccine efficacy and the corresponding multiplicity-adjusted two-sided confidence interval will also be provided. Rejection of the null hypothesis (i.e., success in the study) corresponds to the lower bound of the confidence interval exceeding 0% . An exact analysis will be used. Such an analysis will not adjust for extraneous factors such as age and number of lifetime sexual partners.

The estimate of the vaccine efficacy will account for the follow-up (i.e., person-time at risk) in the vaccine and placebo groups. Since the endpoint for the primary analysis is a composite endpoint, any subject who is eligible to be considered as an endpoint according to the HPV 16-related

C. Approaches to Efficacy Analysis (Cont.)

disease definition, the HPV 18-related disease definition, or both will be included in the population at risk for the primary analysis. The method that will be used to compute the follow-up time for each subject in the population at risk is described in Section VII.D.1.c.

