the vaccine and placebo groups. Kaplan-Meier (product limit) estimates of the time-to-event curves and the corresponding 95% confidence intervals will be displayed by treatment group, and the estimated time-to-event curves will be plotted. The time-to-event distributions between the 2 treatment groups will be compared using the log-rank test. The log-rank statistic and the corresponding p-value will be noted on the plot of the curves. For each subject who meets the endpoint definition, the time-to-event will be the time between the subject's Month 7 visit date and the earliest date a tissue sample is collected from the subject which meets the endpoint criterion. For all other subjects, the time between the subject's Month 7 visit date and the date the subject (1) drops out of the study, (2) has definitive therapy, or (3) completes the study will be used in the analysis. The time-to-event analysis will be conducted for the per-protocol and the 3 MITT populations.

d. Correlates of Protection

An exploratory analysis of any breakthrough HPV 16/18-related CIN 2/3 or worse cases (cases of HPV 16/18-related CIN 2/3 or worse in vaccine recipients) will be performed to try to establish the relationship between immune markers and protection from disease endpoints. Specifically, the immune responses in the non-breakthrough vaccinees will be compared with the immune responses in the breakthrough cases at all available time points (i.e., at Months 7, 24, and 48). However, if there are few cases among the vaccine recipients, there may be insufficient information to establish an immune correlate of protection in this study.

Immune markers will be explored using the per-protocol population. However, if the vaccine is highly efficacious, very few primary endpoints will be observed in the vaccine group in the per-protocol analysis. If this is the case, it may be more informative to explore correlates of protection in the second MITT population. This population still includes only initially HPV naïve subjects but is likely to yield the most endpoints in the vaccine group.

e. CIN 1 or Worse

The vaccine efficacy with respect to the incidence of HPV 16- or 18-related CIN 1 or worse and HPV 6-, 11-, 16- or 18-related CIN 1 or worse will be estimated. In addition, the vaccine efficacy with respect

C. Approaches to Efficacy Analysis (Cont.)

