In the primary per-protocol analysis, follow-up for CIN 2/3 and cervical cancer begins following the Month 7 visit. Therefore, each subject's follow-up time will be computed by calculating the number of days between her Month 7 visit date and her final visit date. For cases, the "final visit" will be the first visit at which CIN 2/3 or cervical cancer was detected for the purpose of person-time computation. This value will be converted to person-years by dividing by 365.25. To obtain the total follow-up time in each treatment group, k_v and k_p , the person-years will be summed over all subjects in the given treatment group.

Although the primary analysis is per-protocol and HPV type-specific, all subjects who are eligible for the per-protocol analysis based on at least 1 of the 2 HPV types being analyzed (HPV 16 or 18) will contribute follow-up time to the totals. For the exploratory analysis of all CIN 2/3, all subjects who are eligible for the per-protocol analysis based on at least 1 high-risk HPV type will contribute follow-up time to the totals.

d. Correlates of Protection

In addition to the methods described in Section III.C.3.c. for assessing the anti-HPV serum RIA responses as potential correlates of protection, the odds of developing breakthrough HPV 16/18-related CIN 2/3 or worse may be modeled as a function of the corresponding Postdose 3 RIA titers using a logistic regression model. Length of postvaccination follow-up and study site will be included as additional model terms. Statistical significance of the coefficient for the RIA titer will be an indication that RIA titer is a predictor of breakthrough

D. Statistical Methods (Cont.)

infection. The estimate of the coefficient will indicate the nature of the relationship. If there are few cases among the vaccine recipients, there may be insufficient information to establish an immune correlate of protection in this study.

e. Potential Bias**1) Ascertainment Bias**

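### If the optional breakthrough model is fitted, the study-site terms it must carry cannot be supported by the few titered cases expected, and follow-up enters as a covariate instead of as person-time

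*SAP*

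**What the plan says.** SAP VII.D.1.d states that "the odds of developing breakthrough HPV 16/18-related CIN 2/3 or worse may be modeled as a function of the corresponding Postdose 3 RIA titers", using logistic regression. The model is therefore optional, but its terms are not: "Length of postvaccination follow-up and study site will be included as additional model terms". Significance of the titer coefficient is to be taken as a sign that titer predicts breakthrough. The section closes with a caution: "If there are few cases among the vaccine recipients, there may be insufficient information to establish an immune correlate of protection in this study".

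Four other places bear on this:

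- SAP VII.D.1.c gives the only definition of follow-up time and writes it for the primary per-protocol analysis. For a case, the final visit "will be the first visit at which CIN 2/3 or cervical cancer was detected for the purpose of person-time computation".
- SAP III.C.3.d expects that "if the vaccine is highly efficacious, very few primary endpoints will be observed in the vaccine group in the per-protocol analysis", and then says that "it may be more informative to explore correlates of protection in the second MITT population".
- The Executive Summary (Endpoints) says that the anti-HPV responses at Months 7, 24 and 48 "will only be measured in the subjects participating in the consistency lot substudy".
- SAP III.C.1 sets the total number of events over both arms: "the final analysis will be conducted when at least 29 cases of the primary endpoint have been observed".

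**The concern.** A term for each study site needs events at many sites, and this analysis can use only vaccinees who became cases and also have a Month 7 titer. A site without a case carries no information about the slope. With few cases, the titer coefficient then rests on a handful of within-site comparisons.

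Follow-up is a separate and smaller matter. If the covariate is the quantity defined in VII.D.1.c, a case's value stops at detection, so the covariate is partly determined by the outcome. The SAP treats person-time as exposure when it estimates vaccine efficacy (VII.D.1.a), and the same treatment suits this model.

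The outcome also pools HPV 16 and HPV 18 disease, while the predictor is the corresponding titer. For a vaccinee without a lesion the SAP does not say which titer that is.

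At stake is the reliability of an exploratory statement about an immune correlate, and nothing beyond it.

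**Working it through.** **1. The case counts.** SAP Table 7 gives power of 80/90/97% with 19 cases and 95/99/>99% with 29 cases, at efficacy 80/85/90%. An exact binomial calculation with p = (1 - VE)/(2 - VE), equal follow-up, and success at no more than 4 vaccine cases of 19 or 8 of 29, gives 80.1/90.9/97.6% and 95.9/99.1/99.9%. The plan's figures reproduce to within one percentage point, so the same p can be used for the expected number of vaccine cases.

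**2. Expected breakthrough cases with a titer (per-protocol, final analysis).**

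- VE 80%: 29 × 0.2/1.2 = 4.83 vaccine cases. VE 90%: 29 × 0.1/1.1 = 2.64.
- Share of vaccinees in the consistency lot substudy (I.B.1): 1,500/5,750 = 0.261.
- With a titer: 4.83 × 0.261 = 1.26 and 2.64 × 0.261 = 0.69.
- Treated as Poisson, the chance of 0 or 1 such case is e^-1.26 × (1 + 1.26) = 64% and e^-0.69 × (1 + 0.69) = 85%. The chance of 5 or more is 0.9% and 0.07%.

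At the interim the expectation is 0.83 and 0.45. On these figures a model with titer, follow-up and site terms will usually have no estimate.

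**3. What happens if more cases accrue.** This needs inputs that the SAP does not give. Assumed: 20 to 90 sites, 5 to 10 cases, true slope -0.5 to -1.0 per SD of ln titer, accrual spread over 0 to 1 year, no true site effect. From the SAP: 41 months after Month 7 and 5% dropout per year (VII.A.1), and 1,500 × 0.82 × 0.85 ≈ 1,045 evaluable substudy vaccinees (VII.A.2). A population of 4,000 was also tried. A case's follow-up ends at detection. Sites without a case were dropped.

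Mean estimated slope divided by the true slope, with the SD of the estimate in brackets; true slope -1.0 per SD, 767 to 800 runs per row:

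| Subjects, cases, sites | Titer only | + follow-up | + site | + both (as in the SAP) |
|---|---|---|---|---|
| 1,045, 5, 20 | 1.02 (0.52) | 1.04 (0.54) | 1.12 (0.68) | 1.27 (0.98) |
| 1,045, 5, 60 | 1.05 (0.52) | 1.08 (0.55) | 1.35 (1.11) | 1.53 (1.25) |
| 1,045, 10, 60 | 1.04 (0.37) | 1.06 (0.39) | 1.22 (0.60) | 1.39 (0.84) |
| 4,000, 10, 90 | 1.02 (0.35) | 1.03 (0.36) | 1.10 (0.43) | 1.20 (0.52) |

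Over all settings with 5 to 10 cases, the SAP's model gives about 1.0 to 1.6 times the true slope and an SD 1.1 to 2.8 times that of titer only. Up to 26% of fits fail to converge at 5 cases. With 40 cases over 20 sites the ratio is 1.0 and the SD about 1.05 times. Follow-up alone gives 1.00 to 1.11; site alone gives up to 1.38. Follow-up adds to the distortion once the site terms are in.

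The medians are closer to the truth: 1.13, 1.29, 1.25 and 1.15 in the four rows. Part of the mean inflation comes from extreme fits. Cox and titer-only logistic models perform about the same (for 1,045 subjects, 10 cases and 60 sites: 1.02, SD 0.36, against 1.04, SD 0.37).

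**4. No true association.** With 1,040 women, 60 sites and slope 0, the SAP's model gave a mean slope of 0.00 at 5 cases and -0.05 at 10. Two-sided 5% rejection was 3.7% and 7.9%. With slope -0.5, power was 14% against 26% for titer only at 5 cases, and 36% against 45% at 10.

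**The case against.** The strongest reply is that the SAP already limits the harm. The analysis is exploratory and the model optional. The main approach in III.C.3.d compares immune responses of breakthrough cases with those of other vaccinees, and the warning about few cases appears in both sections. The text does not say that site enters as one fixed term per centre, and it does not say that follow-up length is the VII.D.1.c quantity. Efficacy summaries elsewhere are type-specific, so a type-matched titer is a natural reading.

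Much of this stands, and it keeps the point small. It does not remove it. The caution gives no minimum number of cases, no sparse-data method and no instruction to drop terms. The second MITT population may add cases, but the titer restriction and the covariates stay the same. The pooling rule in VII.D.2.f belongs to the immunogenicity methods and counts subjects per group, not cases. Elsewhere the SAP recognises the difficulty: the primary analysis adjusts for no extraneous factors (III.C.1), and VII.D.1.g concedes that small case numbers limit what can be done by site.

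A reader might infer that the plan inflates the slope by some fixed amount, such as 40% with a doubled SD. The documents do not support that. Such values arise only with about 5 to 10 cases over 60 to 90 sites, and neither the number of sites nor a slope is in the SAP. A reader might also blame follow-up first; alone it moves the slope by only a few percent.

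**Conclusion.** The specification is poorly fixed, in an exploratory analysis. In the per-protocol population the likely consequence is no estimate at all, because only about 0.7 to 1.3 titered breakthrough cases are expected. This rests on 29 cases, efficacy of 80% to 90%, equal follow-up, and the substudy holding 1,500 of about 5,750 vaccinees. The SAP gives no case count for the second MITT population.

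If 5 to 10 cases do accrue, the slope is pushed away from zero by roughly 0% to 60%, its SD widens roughly 1.1 to 2.8 times and power falls. Study site is the main cause. These ranges rest on the assumed numbers of sites and cases and on the assumed slope.

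It would go too far to say that the model manufactures a correlate. With no association there was no systematic bias, and at most a modest excess of false positives at 10 cases. Nor does the material show that logistic regression must be replaced. No primary or secondary conclusion is affected.

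**What to change.** In SAP VII.D.1.d:

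1. Delete the study-site term, or use region at most.
2. Delete follow-up as a covariate. Enter it as a log person-time offset or as the time axis. A titer-only logistic model performs about the same and would also do.
3. Relate HPV 16 disease to anti-HPV 16 and HPV 18 disease to anti-HPV 18, so that every vaccinee has a defined titer for each outcome.
4. State in advance what is done when cases are too few for an ordinary model: a penalized or exact method, or only a listing of the cases' titers against the distribution in vaccinees. The threshold is for the sponsor to choose; nothing in the SAP determines a number.

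The cost is one reworded paragraph, with no change to data collection or procedures. The downside is that site differences are not adjusted for, which the expected number of cases could not support in any event.
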